#### 4.1.2.2 Primary Hypothesis and Analysis

Once the criterion for “significant gain” in HUI3 is defined, the baseline characteristics of those meeting and not meeting the criterion can be compared. Then it can be hypothesised that those characteristics which are divergent for the group may influence significant gain in HUI3 scores.

Typical factors to consider are etiology, age, duration of hearing loss/deafness, onset of hearing loss, use of hearing aids, tinnitus status, and dizziness status. There are too many etiology categories compared to the total N of subjects so they will be grouped as in Table 1.

For the effects of age, continuous variable or range groups may be evaluated (i.e. approximate ABS age as in Section 1 above will be used unless sample sizes are too small).

Onset of deafness in childhood, or “congenital” deafness may be calculated from age and duration of hearing loss. In consultation with the centre, “pre-linguistic” onset of deafness is

[figure not shown]
defined as <10 years of age. Arguably “congenital” deafness should be limited to ages <2 (for the purposes of identification). The other defined onsets are progressive and sudden HL.

Table 1. Etiologies (implanted ear) at baseline grouped for ZA-01.

Familial	7
Vestibular ( Large vestibular aqueduct Menieres syndrome)	8
Meningitis	8
Viral, (measles and mumps rubella)	9
Ototoxic drugs	11
Middle ear: Cholesteatoma, Congenital atresia, Otosclerosis	15
Other	27
Unknown	75

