## 4 FACTORS INFLUENCING QOL OUTCOMES WITH CI

To differentiate from previous publication the approach will be to establish odds of improvement in HUI Mk III scores. The minimum clinically important change/difference in HUI3 is 0.03 units, but an alternative higher cut-off may be used (or in addition, see below). The aim is to give recommendations on the characteristic/s which are most likely to provide significant health utility from a CI.

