### 4.1.2 Analyses

A logistic regression approach will be used to determine which factors may significantly influence gains in HUI3 scores.

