#### 4.1.5 Presentation of data

The report will conform to a conventional format with data completeness and population summaries (such as demographics).

Summary statistics will be provided for baseline characteristics for those patients reaching the 0.1 HUI3 gain at visit 1, and those who did not. Similarly, for those with baseline HUI hearing attribute categories  $\leq 3$  and those  $>3$ .

Univariate logistic models will be produced with estimated odds ratios and p-values will be presented. If feasible, multivariate logistic models will be produced. In addition, the predictive

capability of the model can be tested, and/or the threshold criterion varied (e.g. via RoC) to obtain higher predictive power.

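### SAP Section 4 takes its primary hypotheses from whichever baseline characteristics diverge between HUI3 responders and non-responders, with no fixed factor list, multiplicity rule or exploratory label

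*SAP*

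**What the plan says.** Section 4 of the SAP states its purpose as "The aim is to give recommendations on the characteristic/s which are most likely to provide significant health utility" from a cochlear implant. Section 4.1.2 names the method: "A logistic regression approach will be used to determine which factors may significantly influence gains in HUI3 scores".

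Section 4.1.2.2, headed as the primary hypothesis and analysis, sets the order of work. Once a criterion for HUI3 gain is chosen, "the baseline characteristics of those meeting and not meeting the criterion can be compared". The next sentence turns the result into the hypotheses: "Then it can be hypothesised that those characteristics which are divergent for the group may influence significant gain in HUI3 scores". A list follows: "Typical factors to consider are etiology, age, duration of hearing loss/deafness, onset of hearing loss, use of hearing aids, tinnitus status, and dizziness status". Etiology is reduced to the eight groups of that section's Table 1. Age coding is left open: "For the effects of age, continuous variable or range groups may be evaluated". Several onset definitions are discussed and none is made final.

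Section 4.1.5 provides summary statistics of baseline characteristics for patients who did and did not reach a gain of 0.1. It adds: "Univariate logistic models will be produced with estimated odds ratios and p-values will be presented". Multivariable models follow if feasible.

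Section 4.1.1 describes one source of data, a single centre with about 110 paired records. Section 4 mentions no validation sample, multiplicity adjustment, significance level or exploratory status.

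**The concern.** A hypothesis obtained by looking at which characteristics differ by outcome cannot be tested at face value on the same outcomes. A univariate logistic model of response on a factor largely repeats the comparison of that factor between responders and non-responders. If the comparison decides which factors go forward, the later p-value no longer has its nominal meaning and the odds ratio tends to lie too far from 1.

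This matters because the stated product is recommendations about who benefits. Elsewhere the SAP is explicit on these points: Section 2.3.2 rules out formal testing for the device description, and Section 1.3.2.2 specifies Tukey comparisons for age groups. Section 4 has no equivalent statement. The SAP Introduction also says that deviations need not be reported, so a reader of the publication might not learn how the factors came to be chosen.

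The problem does not depend on changing the gain cut-off after seeing results, which the SAP also allows. The calculations for this point hold the cut-off at 0.1.

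**Working it through.** **1. The plan's own statistic.** Section 4 gives no error rate or power for the factor tests. Its one reproducible result is the paired t-test in Section 4.1.2.1: mean 0.1490534, 95% CI 0.09963182 to 0.19847490, t = 5.9659, df = 132.

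- SE = (0.19847490 − 0.09963182) / (2 × 1.978) = 0.02498
- t = 0.1490534 / 0.02498 = 5.966, two-sided p = 2.1e-08
- SD of change = 0.02498 × √133 = 0.288

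This agrees with the SAP. It implies 133 pairs, as does the total of Table 2 in Section 4.1.2.3, against about 110 in Section 4.1.1. Both sizes are used below.

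**2. If all listed factors are modelled.** Inputs: seven factors (Section 4.1.2.2), one overall test each, and a two-sided 5% level. That level is in Protocol Section 12.1; using it here is an assumption. With no true effects and independent factors, the chance of at least one p < 0.05 is 1 − 0.95^k:

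| k | Chance |
|---|---|
| 5 | 22.6% |
| 7 | 30.2% |
| 10 | 40.1% |

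Five is shown because childhood onset may be derived from age and duration. Counting those three linked factors as one leaves 7 − 2 = 5. Ten is shown because the list is introduced only as typical.

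**3. If divergence selects.** A simulation (2,000 runs per sample size) drew gain from Normal(0.149, 0.288), cut at 0.1. It used seven independent factors with no effect: etiology in eight groups with the Table 1 shares, two continuous, one with three groups and three binary. Each factor was screened by t-test or chi-square, then tested by univariate logistic likelihood ratio. The SAP does not define divergence, so two screening levels are assumed.

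| Quantity (all factors null) | N = 110 | N = 133 |
|---|---|---|
| At least one factor divergent (p < 0.05) and significant | 28.6% | 32.8% |
| Logistic p < 0.05, given divergent at p < 0.05 | 99.9% | 100% |
| Logistic p < 0.05, given divergent at p < 0.10 | 55% | 57% |
| Most divergent factor significant, same patients | 32% | 36% |
| Most divergent factor significant, fresh outcomes | 6.0% | 5.5% |

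Without selection, each factor's false-positive rate was about 4% to 7%, except etiology at 7% to 8% because of sparse groups. The sparse groups explain part of the excess over 30.2% in some cells. Simulation error is about 1 percentage point near 30%: √(0.3 × 0.7 / 2000) = 0.010. The bias in the odds ratios was not quantified.

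**4. Cost of adjustment.** Take an assumed binary factor with 50% prevalence and response of 40% versus 65%, N = 110 (55 per group).

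- Standard error under the null: √(2 × 0.525 × 0.475 / 55) = 0.0952
- Standard error under the alternative: √((0.24 + 0.2275) / 55) = 0.0922
- Power = Φ((0.25 − z × 0.0952) / 0.0922)
- At 0.05 (z = 1.96): 75%
- At 0.05/7 = 0.0071 (z = 2.69): 47%

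Testing at 0.05 in a 55-patient validation half gives 46%.

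**The case against.** A reader might infer that the Section 4 p-values are circular as planned, with the same test done twice on the same patients. The documents do not establish that. No sentence restricts the logistic models to divergent factors, sets an entry rule or defines divergence by a test. Section 4.1.5 presents the responder and non-responder groups by summary statistics and attaches p-values only to the logistic models. Looking at a descriptive table and then fitting every listed factor leaves each model's p-value as it was. The 99.9% and 55% figures therefore hold only under screening rules that the SAP does not contain.

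Nor does the 30% measure circularity. It is ordinary familywise error, and would be the same for seven factors fixed in advance. It is also an approximate upper figure, since onset, age and duration are linked. Adding baseline hearing class as an eighth factor would raise it, but Section 4.1.2.3 places that under the secondary hypotheses.

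Finally, the wording of Section 4.1.2.2 is tentative and reads like factor-finding, where unadjusted estimates with confidence intervals and an exploratory label are defensible.

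All of this stands. It does not remove the point. The text still defines the primary hypotheses by what diverges, offers the factor list only as typical, and commits to neither reading. Testing in the same patients is an inference, but only one dataset is described and no split is mentioned.

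**Conclusion.** The concern holds in conditional form. Section 4.1.2.2 forms its primary hypotheses from the outcome comparison, and Sections 4.1.2 and 4.1.5 test factors with unadjusted p-values on the only data described.

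- If divergence governs which factors are modelled, emphasised or entered in a multivariable model, the results for those factors are biased by selection. In the simulation, the most divergent null factor was significant in 32% to 36% of runs in the same patients, against about 6% with fresh outcomes.
- If all seven factors are modelled and reported, individual p-values are near nominal. What remains is unadjusted multiplicity: up to about 30% for seven independent factors, about 23% for five.

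These figures assume a 5% level, no true effects, one overall test per factor and independence. The first also rests on the assumed factor distributions. An unconditional claim of circularity goes further than the text allows.

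**What to change.** In SAP Section 4.1.2.2, replace the sentence that derives hypotheses from divergent characteristics with text such as:

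> The candidate factors are etiology (eight groups, Table 1), age, duration of hearing loss, onset, hearing aid use, tinnitus and dizziness, each with the single coding stated here. All are modelled and reported with odds ratios and 95% confidence intervals, whether or not they differ between responders and non-responders. That comparison is descriptive and does not determine entry to any multivariable model.

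State the one coding for age (continuous or grouped) and one set of onset categories. Also state the analysis population, given 110 versus 133 pairs.

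Then choose one of two routes:

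- Label the analysis exploratory and soften the recommendations aim in the opening of Section 4 to match.
- Keep the aim and adjust across the seven factors, for example by Holm.

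Either route needs SAP wording only and no new data. The cost is that fewer factors can be presented as established predictors. Adjustment also loses power: 75% to 47% at the Bonferroni level in the example above. Holm is never less powerful than Bonferroni, but its first step uses the same threshold. For that reason adjustment is offered as an option.

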## 4.1 Statistics

### 4.1.1 Sample Size

The decision of success/fail in significant impact of CI on HUI3 scores requires paired pre/post data in order to test the difference scores. Currently one centre has good follow-up, ZA-01, and overall a high number of patients with 161 at baseline and 117 at 1 year as of December 2019. Thus approximately 110 datapoints are available.

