#### 4.1.2.1 Pass/Fail Criteria

[figure not shown]
The minimum clinically important change/difference in HUI3 is 0.03 units. For HUI3 this change is very small and larger mean differences are typically observed. As such for these analyses we are interested in differences/changes of at least 0.1 units. Below is summarised the simple paired comparison of baseline versus 1-year HUI3 scores:

```
> t.test(dat.w.temp$hui.v3.score.multi.1,dat.w.temp$hui.v3.score.multi.0, p
aired=TRUE)
```

```
Paired t-test
```

```
data: dat.w.temp$hui.v3.score.multi.1 and dat.w.temp$hui.v3.score.multi.0
t = 5.9659, df = 132, p-value = 2.105e-08
alternative hypothesis: true difference in means is not equal to 0
95 percent confidence interval:
 0.09963182 0.19847490
sample estimates:
mean of the differences
      0.1490534
```

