### Histogram of dat.w.temp\$hui.v3.score.multi.1 - dat.w.temp\$hui.v3.score.mul

The mean difference score is 0.149, with a confidence interval of ~0.1 to ~0.2. As stated above, 0.1 is generally considered to indicate a highly significant individual gain in HRQoL. Based on the histogram above, somewhat more than 50% of cases achieved a HUI3 gain of >0.1. An approximate cut-off representing 50% of cases is a good basis for a success/fail criterion for a logistic analysis (i.e. median gain in HUI3 for example). However, it may be useful to tune the criterion to improve the predictive performance of the model once initial results are obtained for gain = 0.1.

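### The Section 4 etiology grouping keeps eight levels, five with about 5 to 9 expected analysable patients, so the planned univariate odds ratios for those levels will be very imprecise and may not be estimable

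*SAP*

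**What the plan says.** SAP Section 4.1.1 bases the analysis on one centre, ZA-01, with "161 at baseline and 117 at 1 year as of December 2019", and concludes: "Thus approximately 110 datapoints are available". Section 4.1.2.1 then prints a paired t-test with "t = 5.9659, df = 132, p-value = 2.105e-08", which means 133 pairs. The text after the histogram takes a gain of 0.1 as the starting success criterion because "somewhat more than 50% of cases achieved a HUI3 gain of >0.1".

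Section 4.1.2.2 lists seven candidates: "Typical factors to consider are etiology, age, duration of hearing loss/deafness, onset of hearing loss, use of hearing aids, tinnitus status, and dizziness status". On etiology it says: "There are too many etiology categories compared to the total N of subjects so they will be grouped as in Table 1". The table is captioned "Table 1. Etiologies (implanted ear) at baseline grouped for ZA-01", so its counts are of baseline patients and not of patients with paired scores.

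Section 4.1.5 commits to univariate logistic models reported with odds ratios and p-values. For anything larger it says: "If feasible, multivariate logistic models will be produced". Section 4 gives no test of feasibility, minimum level size, rule for merging etiology further, or penalised or exact method. It does allow age groups to be dropped when samples are small, but has no such clause for etiology.

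**The concern.** The SAP recognises that etiology has too many categories for the sample, but its remedy is judged on baseline counts. Losing about a third of patients before the paired analysis shrinks levels that are already small, and each is then split into success and failure. An ordinary logistic model then gives very wide intervals for these levels. Where a level is all success or all failure, it gives no finite odds ratio at all.

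Section 4 aims to recommend which patient characteristics make a health-utility gain most likely. With no true effect, an eight-level model on this sample will often show at least one striking etiology odds ratio, and that could be read as a finding.

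**Working it through.** **Inputs.** Etiology counts come from Section 4 Table 1: 7 + 8 + 8 + 9 + 11 + 15 + 27 + 75 = 160, against 161 baseline patients in Section 4.1.1. The number of pairs N is about 110 (Section 4.1.1) or 133 (t-test df 132 + 1; Section 4 Table 2 also sums to 133).

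**The plan's own figure.** SD of the gain = 0.1490534 / 5.9659 × √133 = 0.288. With it, the printed interval (0.0996 to 0.1985) and p-value (2.10e-08) reproduce. A normal approximation gives P(gain > 0.1) = 0.57. The SAP itself says only somewhat above 50%, so I use 50% to 57%.

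**Expected patients per level** = count × N/160, assuming follow-up is unrelated to etiology and, at 133, the same etiology mix. **95% CI factor against Unknown** at 50% success = exp(1.96 × √(4/n + 4/n_Unknown)).

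| Level | Baseline | n at 110 | CI factor at 110 | n at 133 | CI factor at 133 |
|---|---|---|---|---|---|
| Familial | 7 | 4.8 | 6.5 | 5.8 | 5.5 |
| Vestibular | 8 | 5.5 | 5.8 | 6.6 | 4.9 |
| Meningitis | 8 | 5.5 | 5.8 | 6.6 | 4.9 |
| Viral | 9 | 6.2 | 5.3 | 7.5 | 4.6 |
| Ototoxic drugs | 11 | 7.6 | 4.6 | 9.1 | 4.0 |
| Middle ear | 15 | 10.3 | 3.8 | 12.5 | 3.4 |
| Other | 27 | 18.6 | 2.9 | 22.4 | 2.6 |
| Unknown | 75 | 51.6 | reference | 62.3 | reference |

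For a level of 5 against 52, SE(log OR) = √(4/5 + 4/52) = 0.94. The odds ratio needed for 80% power is about exp((1.96 + 0.8416) × 0.94) ≈ 14.

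**Chance of no finite estimate.** A level of size n is all success or all failure with probability p^n + (1 − p)^n; for n = 5 and p = 0.5 this is 6%. Across the eight levels, with the followed-up patients drawn at random from the 160, the chance that at least one is all-or-none is 27% to 31% at N = 110 and 12% to 15% at N = 133 (p from 0.50 to 0.57). Holding each level at its rounded expected size gives 16% to 20% and 8% to 11%. The rest comes from chance variation in which patients are followed up.

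**Simulation** (1,500 data sets per setting, no true effect, 55% success, N = 110). The univariate eight-level model was not estimable in 31% of fits. Where it was, the most extreme etiology odds ratio was typically about 4-fold from 1.

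**Multivariable model, if run.** Coefficients: etiology 7, age 4 (five groups) or 1 (continuous), duration 1, onset 2, hearing aid 1, tinnitus 1, dizziness 1, making 17 or 14. Linear duration and binary hearing-aid, tinnitus and dizziness terms are my assumptions. Smaller outcome class = N × (1 − p).

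- N = 110: 47.3 to 55 events. 47.3/17 = 2.8 and 55/17 = 3.2; 47.3/14 = 3.4 and 55/14 = 3.9.
- N = 133: 57.2 to 66.5 events. 57.2/17 = 3.4 and 66.5/17 = 3.9; 57.2/14 = 4.1 and 66.5/14 = 4.75.

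In simulation with 17 coefficients, N = 110 and assumed covariate distributions, 29% of fits were not estimable.

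**The case against.** The strongest reply is that the SAP commits only to univariate models. The seven factors are ones to consider and not a fixed covariate set, and the multivariable model is conditional. That stands. The events-per-coefficient figures describe a model that the SAP permits but does not promise, so the fair criticism there is that feasibility is undefined.

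Several stronger readings are also not supported:

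- A reader might infer that etiology cannot yield any interpretable odds ratio. Middle ear and Other, with CI factors of about 3.8 and 2.9, are imprecise but usable. At N = 110, roughly 70% of data sets would have no all-or-none level.
- A reader might infer that etiology takes degrees of freedom from the other factors. In univariate models it takes none, and a two-level factor such as tinnitus does not share this sparsity.
- The position of etiology at the head of the list implies no ranking.

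The level sizes are also projections, since the SAP does not give paired counts by etiology. Differential follow-up could make some levels larger and others smaller. None of this changes the position of the five small levels in a model that the SAP firmly plans.

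**Conclusion.** The point holds for the univariate etiology model. For the five smallest levels, serious imprecision is close to certain at either sample size: CI factors are 4.6 to 6.5 at 110 pairs and 4.0 to 5.5 at 133. Outright non-estimability is a material risk and not a certainty. For the conditional multivariable model, the supported statement is about 2.8 to 4.75 events per coefficient with no rule for deciding whether to fit it.

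The figures assume follow-up unrelated to etiology and a success rate of 50% to 57%. Sections 4.1.2.1 and 4.1.5 also allow the success threshold to be tuned; moving it away from the median would shrink the smaller class and worsen them. The 133 pairs exceed the 117 ZA-01 patients with one-year data, so they come from another set or data cut. The SAP does not say which set the models will use.

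**What to change.** 1. Before looking at outcomes by etiology, merge it into three or four groups and record the grouping. As an example, pooling the six named causes (7 + 8 + 8 + 9 + 11 + 15 = 58) gives named, Other and Unknown. At N = 110 the named group has 58 × 110/160 = 39.9 patients, and its CI factor against Unknown is exp(1.96 × √(4/39.9 + 4/51.6)) = 2.3. Non-estimable fits fell to 0% in simulation.
2. Use Firth's penalised logistic regression for models that contain etiology and for any multivariable model. This does not replace merging: with all eight levels and 17 coefficients at N = 110, it cut non-convergence to about 1% but left the CI factor at about 9. It restores estimability, not precision.
3. Say what makes a multivariable model feasible, and in it use continuous duration and continuous age, the latter already allowed by Section 4.1.2.2. With three etiology groups this leaves 2 + 1 + 1 + 2 + 1 + 1 + 1 = 9 coefficients, or 47.3/9 = 5.3 to 55/9 = 6.1 events per coefficient at N = 110.
4. State which paired set is analysed, about 110 or 133, and tabulate etiology within it.

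The cost is a few lines of SAP text and a standard R package. The real loss is coarser etiology groups that combine clinically distinct causes, with no separate odds ratio for each rare cause. Those can still be described by counts.

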**4.1.2.3 Secondary Hypotheses**

One factor which might influence HUI3 gain is the baseline HUI3 score. However, much of the HUI3 multi attribute score variation in this population is produced by the 6-point Hearing attribute (figure below – all CI subjects pre and post scores). This allows us to avoid comparing baseline and gain directly in HUI3 scores (partially correlated).

The hearing attribute can be divided into two broad classifications:  $\leq 3$  (0.71-1 in the figure), where all three indicate that the subject can understand what is said in a group conversation with at least three other people, with or without using a hearing aid, and  $>3$  (0-0.48), the converse, including not hearing at all either one-on-one or with three other people.

Table 2. Numbers of patients in HUI3 Hearing attribute categories 1-6; baseline rows, at visit 1 columns.

Value	6	5	4	3	2	1	Status classification
6	4	7	0	22	2	2	No hearing
5	4	9	1	31	1	1	Group No/with HA
4	0	0	0	2	0	0	Group No/with HA
3	2	3	0	32	1	2	Group OK/with HA
2	0	1	0	1	0	0	Group OK/with HA
1	0	0	1	3	0	1	Group OK/No HA

The baseline hearing attribute classification may be correlated with demographic characteristics and thus it is worthwhile to test this, as well as the influence of baseline hearing attribute on gain in multi-attribute score.

We see that 32 subjects are in category 3 both at baseline and at visit 1. The SSQ scores can be used to evaluate with more precision whether this group benefitted from cochlear implantation. Also the HUI3 multi-attribute score may indicate some change.

Thirdly, to look at the outcome questions in IROS such as whether an improvement in hearing was noted by patients.

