12.1 Statistical Method

Review of the study design was undertaken by an independent statistical consultant, [REDACTED] [REDACTED] Subsequently a proposal for the data analysis methods was made and is available as a separate report upon request (in English only).

In summary, based on the specified hypotheses assuming a 2-sided alpha error of 5%, (95% confidence interval) comparison of intra-subject performance outcomes rated via SSQ and HUI Mark III at preimplant to postimplant annual 1 and 2 years follow up intervals will require data for a minimum of **50** recipients with the same device to determine significant changes due to treatment effects.

13 Administrative Procedures of the Registry

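### SAP Section 4 replaces baseline HUI3 with the baseline hearing attribute, which stays coupled to HUI3 gain, and requires no baseline-adjusted estimate, so a factor that only marks room to improve may appear as a predictor of benefit

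*SAP*

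**What the plan says.** SAP 4.1.2 sets the method: "A logistic regression approach will be used to determine which factors may significantly influence gains in HUI3 scores". Success is first defined as a gain of 0.1, and the cut-off may be tuned "once initial results are obtained for gain = 0.1" (SAP 4.1.2.1).

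The candidate list in SAP 4.1.2.2 does not contain baseline HUI3: "Typical factors to consider are etiology, age, duration of hearing loss/deafness, onset of hearing loss, use of hearing aids, tinnitus status, and dizziness status".

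SAP 4.1.2.3 then raises it: "One factor which might influence HUI3 gain is the baseline HUI3 score". It goes on to say that "much of the HUI3 multi attribute score variation in this population is produced by the 6-point Hearing attribute", and draws the conclusion "This allows us to avoid comparing baseline and gain directly in HUI3 scores (partially correlated"). The same section plans to test the baseline hearing class against demographic characteristics and against gain in the multi-attribute score.

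On model form, SAP 4.1.5 states: "Univariate logistic models will be produced with estimated odds ratios and p-values will be presented". Multivariate models follow only if feasible, and no covariates are listed for them. Nothing in Section 4 requires a factor's odds ratio to be adjusted for baseline HUI3 or for the hearing class.

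**The concern.** Gain is follow-up minus baseline, so anything that measures baseline tends to correlate negatively with gain. Patients who start low have room to rise and regress upward. Patients who start high have little room and regress downward. Swapping the total score for one of its components does not break that link. The more of the score's variation the component carries, the more of the link it keeps, so the SAP's reason for choosing the attribute is also the reason it cannot serve this purpose.

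What is at stake is the aim in the opening paragraph of Section 4: recommendations on which patient characteristics go with worthwhile health utility from an implant. If a characteristic is associated with baseline HUI3, its unadjusted odds ratio mixes two things: how far such patients have to rise, and whether they do better than others who started at the same level. Only the second is influence on outcome in the sense a reader of those recommendations is likely to assume.

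**Working it through.** **1. Reproduce the SAP's paired test (4.1.2.1).** Mean gain 0.1490534, t = 5.9659, df = 132, so 133 pairs.
- SE = 0.1490534/5.9659 = 0.02498.
- SD of gain = 0.02498 × √133 = 0.288.
- 95% CI = 0.0996 to 0.1985, as printed.

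**2. Re-sum Table 2 of SAP 4.1.2.3** (hearing category at baseline by visit 1). The cells total 133, matching the t-test.

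| Baseline category | n | Improved | Unchanged | Worse |
|---|---|---|---|---|
| 4-6 | 37+47+2 = 86 | 33+34+2 = 69 (80%) | 13 | 4 |
| 1-3 | 40+2+5 = 47 | 3+0+0 = 3 (6%) | 33 | 11 |

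The odds ratio is (69 × 44)/(17 × 3) = 59.5. The five patients in category 1 cannot improve; leaving them out gives 3/42 (7%). At visit 1, 91 of 133 are in category 3, so most patients converge on one level wherever they began. On category numbers, baseline level and improvement correlate 0.73. On the utility scale, the correlation of baseline with change is -0.71 to -0.78 (0, 0.48, 0.71 and 1 taken from the section's ranges; the unstated category 5 varied from 0.05 to 0.43 and category 2 from 0.75 to 0.95).

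This is change in the attribute, not HUI3 gain above 0.1. It shows that the substitute is itself strongly coupled to its own change; the step to HUI3 gain rests on the attribute being a large part of that score.

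**3. Coupling in HUI3 itself.** The documents give no pre-post correlation for the Section 4 patients. The nearest source is Table 2 of SAP 1.3.1: SDs 0.188 pre, 0.168 post, 0.182 change. It is approximate, because N is 29, 38 and 27.
- r(pre, post) = (0.188² + 0.168² - 0.182²)/(2 × 0.188 × 0.168) = 0.0304/0.0632 = 0.48.
- r(pre, gain) = (0.482 × 0.168 - 0.188)/0.182 = -0.59.

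These SDs do not describe the Section 4 data. A gain SD of 0.288 would need r = (0.188² + 0.168² - 0.288²)/0.0632 = -0.31. I therefore also used the 0.288 gain SD, assuming equal pre and post SDs and r = 0.48; this gives r(pre, gain) = -√((1 - 0.48)/2) = -0.51.

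**4. Simulated consequence.** Logistic regression of gain above 0.1 on one factor, at 5% two-sided (Protocol 12.1: "assuming a 2-sided alpha error of 5" per cent; Section 4 states no level). SAP 4.1.1 gives about 110 usable pairs, while the t-test and the hearing table have 133, so both are used. Factor-baseline correlations of 0.2, 0.3 and 0.4 are assumptions.

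| Null hypothesis for the factor | Setting | Unadjusted, significant | Adjusted for baseline HUI3, significant |
|---|---|---|---|
| A: no effect on follow-up given baseline | n = 110, gain SD 0.182 | 14 / 30 / 49% | 4-5% |
| A | n = 133, gain SD 0.288 | 14 / 28 / 45% | 4-5% |
| B: shifts pre and post equally, no effect on gain | n = 110, gain SD 0.182, mean gain 0.12 assumed | 5 / 5 / 4% | 20 / 42 / 69% |

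Across runs, the unadjusted rate under A is about 13-49%. Under B, a further set of runs put the adjusted rate at about 13-50%, against about 5% unadjusted.

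**5. Would adjusting for the hearing split be enough?** Take a binary factor that shifts baseline by 0.5 or 0.8 SD under null A, n = 110, pre-post correlation 0.3 to 0.7, and an assumed 0.8 correlation between the attribute and baseline HUI3.

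| Adjustment | 0.5 SD shift | 0.8 SD shift |
|---|---|---|
| None | 12-22% | 25-51% |
| Two-class hearing split | 8-11% | 12-26% |
| Continuous baseline HUI3 | about 5% | about 5% |

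The split removes only part of the inflation.

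**The case against.** Four points can be made for the plan.

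- **The wording is modest.** The SAP says it avoids a direct comparison and itself notes the partial correlation. A reader might infer that it claims to have removed the coupling altogether; it does not say so. This stands, and the sentence needs correcting rather than condemning.
- **The baseline-adjusted model is not neutral.** Null A makes it correct by construction. Under null B it produces the false predictors. In observational data the two models answer different questions, and the documents do not show which null fits any factor. This stands, and it rules out simply replacing every unadjusted model.
- **The aim is partly predictive.** SAP 4.1.5 speaks of predictive capability. For choosing who is likely to gain, room to improve is genuine information. This stands for prediction, but not for statements that a factor influences gain, which is how SAP 4.1.2 words the purpose.
- **There is partial handling.** The hearing class is to be tested against demographics and gain, characteristics are summarised by hearing class, the 32 patients unchanged in category 3 get a closer look with SSQ, the factor list is open, and multivariate models are possible. These steps could reveal the problem, but none commits the analysis to an adjusted odds ratio.

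A reader might also infer that factors tracking baseline will be reported as predictors. The documents do not support that. They show no correlation between any candidate factor and baseline HUI3; the SAP says only that the hearing class may be related to demographics. Even under null A, such a factor is non-significant in at least half the simulated trials.

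**Conclusion.** The point holds in a limited form. The hearing attribute does not take the analysis out of the baseline-gain coupling, and Table 2 of SAP 4.1.2.3 shows how strongly the attribute is tied to its own change (80% against 6% improving). Since no baseline-adjusted estimate is required, a factor associated with baseline may look like a predictor of gain only because it marks room to improve.

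The size is conditional: about 13-49% false positives unadjusted against 4-5% adjusted, for factor-baseline correlations of 0.2 to 0.4, a pre-post correlation of about 0.48 borrowed from a small Section 1 sample, and no effect on follow-up given baseline. With equal shifts in pre and post scores the inflation moves to the adjusted model. The defect is thus an unstated question and an incorrect rationale; the documents do not establish that the unadjusted models are wrong for every purpose.

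**What to change.** In SAP 4.1.2.3, replace the sentence with a statement that the hearing attribute is part of HUI3, does not remove the coupling, and that its association with gain largely reflects room to improve.

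In SAP 4.1.2.2 and 4.1.5, prespecify:

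- for each factor, the unadjusted odds ratio beside one adjusted for continuous baseline HUI3;
- a supporting linear regression of 1-year HUI3 on the factor plus baseline HUI3, in the same pairs;
- the question each answers: who gains most (unadjusted), and who does better at equal baseline (adjusted);
- that recommendations about influence on outcome rest on factors that hold at equal baseline;
- the number of patients who start too high to gain 0.1.

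The cost is SAP wording and a second set of estimates. Every pair already has a baseline HUI3 score, so no new data are needed. The adjusted odds ratios apply only at equal baseline, and the report must say so.
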